Title of the study: CYP2D6 polymorphism defining UM, IM, NM and PM status in unselected medically treated patients of general practice in Austria

NCT03859622

Date of document: October 9, 2018

STUDY PROTOCOL

1 Background

The hepatic CYP2D6 enzyme metabolizes a significant number of drugs frequently prescribed in general practice/ family medicine. Various genetically different variants define if the patient is an ultra-rapid (UM), an extensive (EM) (the normal case), an intermediate (IM) or a poor metabolizer (PM). It is estimated that approximately 20- 25 % of frequently prescribed drugs are activated to more active or metabolized to ineffective or less effective drugs by CYP2D6. Substrates of CYP2D6 are mainly antidepressants, neuroleptics, opioids (e.g. codeine), beta-blockers, anti-arrhythmic drugs and various other single drugs. In case of an UM a drug can be metabolized too rapidly losing its therapeutic effect, requiring a higher dosage, or it can have a toxic effect, if it is converted too rapidly into the effective form (e.g. codeine). If metabolized too slowly (PM) it can accumulate and reach toxic levels.

Up to now data with respect to the frequency and distribution of the various types of metabolizers (UM, NM, IM, PM) in Austrian General Practice in patients prescribed drugs primarily metabolized by CYP2D6 are sparse.

2 Primary and secondary aims of the study

The primary aim of the study is to generate data on CYP2D6 polymorphism in patients of an average Austrian general practice, which allows to group patients according to their EM, UM, IM and PM status, which is of considerable practical relevance for deciding, which drug to choose. For this reason we describe the number and distribution of frequent and clinically relevant CYP2D6 alleles including copy number variations as well as the genotype-predicted phenotype in patients of the respective general practice.

In addition this study tries to investigate in how many patients the knowledge of the CYP2D6 metabolizing status would have been of clinical relevance with respect to the actually prescribed drug.

As a secondary aim, data relating to the total number of patients of the respective Austrian general practice having been prescribed one or more drugs within the last 3 years, mainly metabolized by CYP2D6 or being an inhibitor of it, are collected by extracting electronic records of the practice. In addition the average percentage of drugs metabolized by CYP2D6 in relation to the number of all prescribed drugs is registered by extracting the electronically stored prescriptions of the last 3 years.

3 Study design

This is an observational cohort cross-sectional study performed in an average Austrian general practice in 2017 and 2018 enrolling 290 unselected consecutive patients visiting the practice office for a routine blood test for various chronic medical conditions. Only in case a patient is actually taking or has been prescribed a drug metabolized by CYP2D6 (or taking a drug which is a strong inhibitor of CYP2D6) within the last 3 years, the genetic polymorphism of CYP2D6 is determined. No further genetic investigations or additional blood collections are performed.

For evaluating the number and characteristics of patients having been prescribed one or more specific drugs within the last 3 years, all relevant demographic and medical data are extracted from their electronic records and de-identified before further processing.

In addition the number of prescriptions (during the last 3 years) of all drugs metabolized by CYP2D6 (or which are strong inhibitors of CYP2D6) as identified by their ATC-code, in comparison to the total number of prescribed drugs of the practice is extracted from the electronic records

Patients who were considered to be eligible to participate in the study have to sign an informed consent after being informed also by orally given information about the aims of the study.

The study was approved by the Ethics Committee of Lower Austria.

4 Selection of patients

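### Do the differing drug sets in Sections 2 and 3, and the unstated place of patients genotyped only for an inhibitor, make the prescription share and the relevance count uninterpretable?

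*Combined protocol and SAP*

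**What the plan says.** Section 2 (Primary and secondary aims) gives the prescription outcome as "the average percentage of drugs metabolized by CYP2D6 in relation to the number of all prescribed drugs", over three years of stored prescriptions. The sentence before it, on the number of patients, has a wider scope: drugs "mainly metabolized by CYP2D6 or being an inhibitor of it".

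Section 3 (Study design) describes the extraction. It takes prescriptions of "all drugs metabolized by CYP2D6 (or which are strong inhibitors of CYP2D6) as identified by their ATC-code". The base is the practice total, since this count is to be viewed "in comparison to the total number of prescribed drugs of the practice". Its sentence on the patient count refers only to patients "having been prescribed one or more specific drugs within the last 3 years". Its genotyping rule covers a patient "actually taking or has been prescribed a drug metabolized by CYP2D6 (or taking a drug which is a strong inhibitor of CYP2D6"; the same three-year window applies. Enrolment is fixed by "enrolling 290 unselected consecutive patients".

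Section 1 (Background) uses another phrase, "drugs primarily metabolized by CYP2D6". Section 10 (Statistics) uses an undefined label for the CYP2D6 drugs in its Spearman comparison with Lower Austria, and says categorical data are summarised as frequencies and percentages. The relevance aim in Section 2 asks in how many patients knowing the status would have mattered for the drug they were actually prescribed. It names no denominator.

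**The concern.** Two things look wrong on a first reading.

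- **Prescription share.** Section 2 counts substrates. Section 3 sets substrates and strong inhibitors together against the practice total. If the Section 3 ratio were reported under the Section 2 description, the share would be too high by whatever fraction of prescriptions are strong inhibitors but not substrates, and a reader could not tell. The changing scope (mainly, primarily or simply metabolized; any inhibitor or only a strong one) adds to the doubt.
- **Relevance count.** A patient who qualifies only through a strong inhibitor may have no substrate for the relevance question to apply to. If the result is given as a percentage, someone must decide whether such patients belong in the denominator, and the plan does not say.

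In a descriptive study the percentages are the result, so an unclear numerator or denominator deserves a check.

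**Working it through.** The plan gives no figure for either quantity, so there is nothing to reproduce. The check compares the definitions and then asks how far the results could move.

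**1. Prescription share**

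Let T be all prescriptions, S the substrate prescriptions, and I the prescriptions of strong inhibitors that are not substrates.

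- Section 2, read as a simple ratio of prescriptions: S/T.
- Section 3 set against the same total: (S + I)/T.
- Difference: I/T, which is zero if every strong inhibitor prescribed is also a substrate.

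Section 2 speaks of an average percentage and does not say what is averaged, so the simple ratio is itself an assumption. The documents do not give I. For illustration only, take S/T as 20% to 25%, the Background's estimate for frequently prescribed drugs, and assume I/T:

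| Assumed I/T | Substrates only | Substrates or strong inhibitors | Relative rise |
|---|---|---|---|
| 1% | 20–25% | 21–26% | 4–5% |
| 3% | 20–25% | 23–28% | 12–15% |
| 5% | 20–25% | 25–30% | 20–25% |

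Both columns come from the same extraction. Each prescription is identified by ATC code, so S and I can be separated without new data.

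**2. Relevance count**

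Let G be the patients genotyped (at most 290), k those genotyped only for an inhibitor, and R the relevant patients among the G − k with a substrate.

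If no inhibitor-only patient is relevant, excluding them multiplies the percentage by [R/(G − k)] / [R/G] = G/(G − k). With G = 290 and assumed k:

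- k = 3: 290/287 = 1.010
- k = 15: 290/275 = 1.055
- k = 29: 290/261 = 1.111

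That covers one direction only. The aim refers to the drug actually prescribed, not to a substrate, and Section 3 treats a strong inhibitor as sufficient reason to genotype. The plan therefore does not rule out counting these patients as relevant. Assuming about 30% relevance among substrate users and G = 290:

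| k | R | Excluded, R/(G − k) | Included, none relevant, R/G | Included, all relevant, (R + k)/G |
|---|---|---|---|---|
| 14 | 83 | 83/276 = 30.1% | 83/290 = 28.6% | 97/290 = 33.4% |
| 29 | 78 | 78/261 = 29.9% | 78/290 = 26.9% | 107/290 = 36.9% |

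The direction is open, and k is not in the documents. If k = 0 the three columns agree.

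**3. What does not move**

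Allele counts, copy number and predicted phenotype are tabulated over everyone genotyped. They depend neither on the prescription numerator nor on the handling of inhibitor-only patients in the relevance count. The Spearman comparison sets the practice's drugs beside the corresponding drugs in Lower Austria, so it compares like with like whichever list is used.

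**The case for a change.** The strongest case for a change is that the difference between Sections 2 and 3 is hard to dismiss as shorthand. In Section 2 the patient-count sentence names inhibitors and the next sentence, on the share, does not. Section 3 joins the two classes with an or, which treats them as distinct, and then sets the joint set against the total. No section promises separate reporting, and no ATC list is given. Stating the drug sets would cost a few lines.

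Much of this stands. The wording does differ, the step from any inhibitor to a strong inhibitor is a real discrepancy, and the place of inhibitor-only patients is unstated. It does not show that a wrong figure would result. Section 2 states the outcome and Section 3 states what is pulled from the records; a wider pull does not redefine the outcome, and inhibitors are needed for the patient count in any case. The Background phrase defines no study variable, and the reference to specific drugs in Section 3 points back to the drugs already described. On relevance, a rule that only substrate patients form the denominator would settle a question the plan leaves open.

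**Conclusion.** The concern identifies a true ambiguity but does not call for a change. It is a gap in detail that an analyst would fill sensibly: take the substrate codes for the Section 2 share, report inhibitors separately if wanted, and give the relevance count beside the number genotyped. Followed as written, the plan still yields interpretable descriptive figures.

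No size can be established from the documents. The illustrative shifts (1 to 5 percentage points in the share; a span of about 5 points in the relevance percentage at 14 inhibitor-only patients and 10 points at 29) rest on assumed counts that may be zero, on a simple-ratio reading of the share, on all 290 patients being genotyped and on about 30% relevance among substrate users. A smaller genotyped group would enlarge the relevance effect for the same number of inhibitor-only patients. The primary allele and phenotype description is unaffected.

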4.1 Inclusion criteria

In principle all patients who are capable of giving a written informed consent and who are visiting the practice due to various medical reasons for a routine blood sampling are suitable to be included into the study.

4.2 Exclusion criteria

Patients who are not capable to give a written consent or who are unable to understand the aim of the study are excluded from the study.

5 Blood sampling and processing of the specimens

A standardized blood sampling using a Vacutainer system with filling of an EDTA tube (4 ml) for the red and white blood count is performed. 300 microliters of the collected blood are used for further determination of the CYP2D6 polymorphism.

6 Isolation of DNA

DNA is extracted from EDTA blood in the practice laboratory by using the Spin Micro Extraction Kit® (ViennaLab, Vienna). The concentration and quality of DNA is measured using a Bio Photometer plus (Eppendorf). The extracted DNA is stored at -81°C in a ultra-low temperature deep freezer (U101-86, New Brunswick Scientific Co., Inc) without any further additives.

7 Real-time PCR for determination of copy number of the CYP2D6 gene

For the determination of the copy number of the CYP2D6 gene a real-time PCR in triplicates on an ABI StepOnePlus by using the CYP2D6 RealFast™ CNV Assay (ViennaLab) is performed in the practice laboratory.

The test is based on the fluorogenic 5' nuclease assay, also known as TaqMan® assay. Each reaction contains gene-specific primer pairs for amplification of CYP2D6 and endogenous control (EC) gene fragments with 141 bp each. Further components are two dual-labeled, gene-specific hydrolysis probes, the FAM-labeled CYP2D6 probe and the HEX-labeled EC probe, which hybridize to an internal sequence of the amplified fragments. The proximity of the 5'-fluorescent reporter and 3'-quencher dye on intact probes prevents the reporter from fluorescing. During the extension phase of PCR the 5' - 3' exonuclease activity of Taq DNA polymerase cleaves the 5'-fluorescent reporter from the hybridized probe. The physical separation of the fluorophore from the quencher dye generates a fluorescent signal in real-time, which is proportional to the accumulated PCR product. The CYP2D6 RealFast™ CNV Assay is a relative quantitation assay and compares the amount of both nucleic acid targets (CYP2D6 and EC) in relation to the CYP2D6 CNV Calibrator. The EC gene is used to

normalize fluorescence signals between different samples and serves as a PCR positive control.

For normalization of data ROX dye to a final concentration of 1 microliter to the 2 x Probe Mix is added.

RT- cycling conditions for the ABI StepOneplus cycler: Initial denaturation: 95°C 10 min 1 cycle; denaturation 95°C 15 sec 40 cycles; annealing /extension 60°C 1 min.

8 PCR and hybridisation for CYP2D6 allele determination by the PGX-CYP2D StripAssay™

This assay is used for a subset of samples in this study and covers only 3 polymorphic loci: 1795delT (2D6*6), 1934G>A (2D6*4) and 2637delA (2D6*3). The test principle and procedure are similar to the PGX-CYP2D6 XL StripAssay® as described below but using different cycling conditions for the Palm-Cycler (Corbett Life Science): pre-PCR: 94°C/2 min; thermocycling: 94°C/15 sec.- 58°C/ 30 sec.-72°C/30 sec (35 cycles); final extension: 72°C/3 min.

9 PCR and hybridisation for CYP2D6 allele determination by the PGX-CYP2D6 XL StripAssay®

For the determination of 19 clinically relevant CYP2D6 alleles (*1; *2 A, *2 B-M; *3, *4A-H, K, L or P, *4J or N, *4M; *5; *6 A, B or D, *6C; *7, *8; *9;; *10A or B, *10 C or D; *11; *12; *14; *15; *17; *29; *35; *39; *40 or *58; *41) a PCR amplification on a Palm-Cycler (Corbett Life Science, Eight Mile Plains, QLD 4113, Australia) using biotinylated primers is first performed. The amplification products are further hybridized to a test strip containing allele-specific oligonucleotide probes immobilized as an array of parallel lines. Bound biotinylated sequences are detected using streptavidin-alkaline phosphatase and color substrates. The evaluation of this reaction is done manually by using the StripAssay®-Evaluator (ViennaLab,Vienna), a proprietary PC program to determine the homozygous or heterozygous genotype.

Cycling conditions for the Palm-Cycler (Corbett Life Science): pre-PCR: 95°C/4 min; thermocycling: 95°C/25 sec.- 60°C/ 45sec.-72°C/1min (36 cycles); final extension: 72°C/3 min.

According to the manufacturer the StripAssay and RealFastCNV Assay results were 100% concordant with genotypes and copy numbers obtained by reference methods and specimens, such as Sanger sequencing, Coriell reference DNA or long-range PCR. The PGX-CYP2D6 XL StripAssay® and the CYP2D6 RealFast™ CNV Assay have been successfully validated on 118 and 98 samples, respectively.

For internal evaluation of validity, sensitivity and specificity the study-laboratory participated successfully in the PGX-CYP2D6XL StripAssay® and CYP2D6 RealFast™ CNV Assay Confirmation Program.

10 Statistics

Statistical Analysis Plan

Statistics

Statistical Analysis

The data are recorded and analyzed using Microsoft Excel Version 10 and the R Language and Environment for Statistical Computing and Graphics, Version 2.9. Standard methods are used for the description of data (frequencies and percentages for categorical data, mean and standard deviation for continuous data). To compare frequencies of CYP2D6-specific drugs prescribed in the single practice with the total number of the respective prescriptions in

Lower Austria, Spearman`s rank correlation-coefficient is calculated. Differences between groups were calculated by paired t-test. A p-value < 0.05 was considered to indicate statistical significance.

The Hardy-Weinberg- equilibrium is calculated using Fisher`s Exact Chi-Square test due to the expected small numbers of genotypes.

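### The primary allele and phenotype proportions are planned without confidence intervals, and no rule says how samples typed on the 3-locus assay count towards the alleles it cannot detect

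*Combined protocol and SAP*

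**What the plan says.** Section 2 makes the primary aim an estimation task. It covers the "number and distribution of frequent and clinically relevant CYP2D6 alleles including copy number variations" and the "genotype-predicted phenotype in patients of the respective general practice".

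The analysis planned for these categorical results, in the Statistical Analysis text under section 10, is: "Standard methods are used for the description of data (frequencies and percentages for categorical data, mean and standard deviation for continuous data". The other methods named there are a Spearman correlation for prescription frequencies, a paired t-test for unspecified groups, and a Hardy-Weinberg test, with an exact method chosen because few patients per genotype are expected. None of them attaches a measure of precision to a primary proportion.

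Two strip assays supply the allele calls:

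- Section 8, on the smaller assay: "This assay is used for a subset of samples in this study and covers only 3 polymorphic loci". These loci define *3, *4 and *6.
- Section 9, on the XL assay: "For the determination of 19 clinically relevant CYP2D6 alleles".

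The plan does not give the subset's size, how its samples were chosen, or whether they were also run on the XL assay. Copy number comes from a separate real-time PCR assay (section 7), described without any restriction to a subset.

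**The concern.** Two things affect how the primary table can be read.

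First, a bare percentage hides how little information stands behind a rare category. Section 1 says that Austrian data are sparse, and section 2 gives the results practical relevance for choosing drugs. The percentages will therefore be used as estimates beyond this sample.

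Second, one percentage rule is applied to samples that may have been tested for different alleles. A sample typed only at three loci says nothing about, for example, *10 or *41. If it stays in the denominator as though those alleles had been looked for and not found, their frequencies are too low and the frequency of *1, the default call, is too high. Where the missed alleles reduce enzyme activity, some patients would be called normal who are not. An interval placed on that denominator would be centred on the wrong value, so the denominator has to be settled first.

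**Working it through.** **Inputs from the documents.** Planned enrolment is 290 (section 3). The 3-locus assay covers *3, *4 and *6 (section 8). The XL assay's allele list is in section 9. The documents give no expected frequencies, no subset share and no precision target for the 290, so there is no precision figure of the plan's own to reproduce. Every proportion and share below is an assumption.

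**Alleles at issue.** Counted by star number, with *40 or *58 as one group, the XL list has 20 groups including *1. Then 20 − 1 − 3 = 16 non-*1 groups lie outside the 3-locus assay. If *5 is taken from the copy-number assay, 15 remain.

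**Precision.** These are exact (Clopper-Pearson) 95% limits: for x out of n, the lower limit is the 0.025 quantile of Beta(x, n − x + 1) and the upper limit is the 0.975 quantile of Beta(x + 1, n − x). When x = 0 the upper limit is 1 − 0.025^(1/n).

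| Patients supporting the estimate (assumed) | Category near 2% | Category near 5% | None observed: upper limit |
|---|---|---|---|
| 290 | 6/290 = 2.1% (0.8 to 4.4%) | 14/290 = 4.8% (2.7 to 8.0%) | 1.3% |
| 145 | 3/145 = 2.1% (0.4 to 5.9%) | 7/145 = 4.8% (2.0 to 9.7%) | 2.5% |

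Wilson limits are close: 0.95 to 4.44% for 6/290 and 0.71 to 5.91% for 3/145.

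**Conditional bias.** Suppose a share s of samples has the 3-locus assay only, assignment is unrelated to genotype, and untested alleles are counted as absent. An allele outside the three loci with true frequency q is then reported on average as q × (1 − s). With all 290 genotyped there are 2 × 290 = 580 chromosomes, of which 580 × (1 − s) were tested for that allele.

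| Assumed s | Chromosomes tested | True 10% reported as | True 5% reported as | True 2% reported as |
|---|---|---|---|---|
| 10% | 522 | 9.0% | 4.5% | 1.8% |
| 20% | 464 | 8.0% | 4.0% | 1.6% |
| 50% | 290 | 5.0% | 2.5% | 1.0% |

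Worked example at q = 10% and s = 20%: about 46 copies are seen. Over 580 this is 7.9% (5.9 to 10.4%); over the 464 tested it is 9.9% (7.4 to 13.0%). If exact intervals were added but the denominator stayed at 580, they would contain the true 10% in 90%, 67% and 0.4% of studies at shares of 10%, 20% and 50%. Over the chromosomes tested the figure is about 96%. For a true 2% allele the coverage over 580 is 97%, 95% and 69%, so the harm is slight for a rare allele unless the subset is large.

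**A denominator that would go wrong.** It may seem natural to keep any 3-locus patient whose result happens to settle the phenotype. That selects on the outcome. Assume 6% poor metabolizers, all carrying two of *3, *4 and *6, and no other conclusive 3-locus result. There are 0.06 × 290 = 17.4 poor metabolizers.

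- At s = 50%: 145 XL patients plus 8.7 conclusive ones gives 17.4/153.7 = 11.3%.
- At s = 20%: 232 + 3.48 gives 17.4/235.5 = 7.4%.

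Both overstate the assumed 6%.

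**The case against.** The strongest reply is that the bias is not in the plan. It needs two conditions that no section states: that the subset never gets the XL assay, and that untested alleles are divided by all genotyped chromosomes. A reader might infer from section 8 that the allele frequencies will be biased. The documents do not support that; they leave the matter open. The subset shares and allele frequencies used above are assumptions, and the coverage figures describe an interval that the plan does not contain. All of this stands, and the point is limited accordingly.

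It can also be said that a descriptive study needs no intervals, because a reader with the count and denominator can compute them. That is partly right: no hypothesis or threshold rests on these proportions. But it works only if the correct denominator is shown for each proportion, which is what the plan leaves unsettled.

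Three stronger readings should not be drawn:

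- **Fewer than 290 are genotyped.** Section 3 describes "enrolling 290 unselected consecutive patients visiting the practice office for a routine blood test for various chronic medical conditions" and then limits genotyping: "Only in case a patient is actually taking or has been prescribed a drug metabolized by CYP2D6" (or a strong inhibitor) within three years. Section 4.1 does not require drug exposure, which suggests a smaller number. But the title's reference to medically treated patients, and section 3's mention of eligible patients giving consent, allow the reading that all 290 qualify. The text is ambiguous.
- **Copy number is ignored.** The strip evaluator is "a proprietary PC program to determine the homozygous or heterozygous genotype", but section 7 puts no subset limit on the copy-number assay. Only an explicit rule for combining the two results is missing.
- **The target population is misstated.** The aim refers to patients of the practice, but the title and section 1 already point to treated patients. This is a matter of wording.

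**Conclusion.** The point holds in a limited form. That no interval is planned for the primary proportions follows directly from the text. Its consequence is real for rare categories even if all 290 are genotyped: an observed 2.1% is compatible with 0.8% to 4.4%.

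The lack of a rule for 3-locus samples is also plain from the text, but the bias it could cause is conditional and its size cannot be known from the documents. It runs from zero, if the subset also had the XL assay, to a halving of affected allele frequencies at an assumed 50% share. The factor (1 − s) further assumes that assay assignment is unrelated to genotype.

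The change should be made because it concerns the primary table and is cheap. Stating the number genotyped beside the 290 is a minor clarification and does not carry the conclusion.

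**What to change.** 1. Report each phenotype and allele proportion with its count, its denominator and an exact (Clopper-Pearson) or Wilson 95% interval. For alleles the denominator is nominally two per tested patient, with a stated rule for counting deletions and duplications. A binomial interval on that count assumes Hardy-Weinberg proportions, which the SAP already plans to test.
2. State the size of the 3-locus subset, how it was selected, and whether it also had the XL assay.
3. If the subset also had the XL assay, no change of denominator is needed.
4. If it had the 3-locus assay only, and assignment did not depend on genotype or on a 3-locus result, use only XL-typed patients as the denominator for all phenotype shares and for alleles outside *3, *4 and *6. Take *5 and duplications from the copy-number assay where it was run. Do not add back 3-locus patients because their result happens to be conclusive.
5. If the XL assay was run as follow-up to a 3-locus result, do not restrict to XL-typed samples. Report *3, *4 and *6 for all patients and label the other alleles as incompletely tested.
6. As a clarification, give the number genotyped beside the 290.

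The cost is SAP and table wording: an interval column, a denominator column, the subset description and a counting rule. No extra patients or assays are needed. The drawback is that fewer than 290 patients may support the phenotype shares and the alleles outside the three loci, so those intervals will be wider.
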